# 2 STUDY OBJECTIVES

# 2.1 Primary Objective

To assess the long term safety and tolerability of BMS-708163 in patients with prodromal Alzheimer's Disease.

# 2.2 Secondary Objectives

To assess the predictive value of CSF biomarkers (A $\beta$ 40, and A $\beta$ 42, total Tau, total Tau/A $\beta$ 42 ratio, and phosphorylated Tau) on progression to dementia.

# 2.3 Exploratory Objectives

1) To explore drug effects on progression to dementia (based on confirmed progression using DSM-IV criteria)

- a) To explore effects of BMS-708163 on brain atrophy rate as measured by volumetric MRI
- b) To explore and prospectively characterize effects the Clinical Dementia Rating scale (including the CDR-Sum of Boxes score and CDR global score), an instrument designed to measure the severity of cognitive symptoms in daily life, as part of the natural course (in placebo patients) and potential impact of BMS-708163
- c) To explore the correlation of APOE status with BMS-708163 pharmacodynamic (PD) effects (such as on biomarkers and cognition)
- d) To explore Aβ42 CSF Screening cut-off value of > 200 pg/mL versus < 200 pg/mL and Total Tau/AB42 ratio ≥ 0.39 with regard to progression rates and biomarker changes in both the randomized and the non-randomized, observational cohort of subjects
- e) To explore the pharmacodynamic effects of BMS-708163 on CSF biomarkers linked to mode of action (A $\beta$ 38, A $\beta$ 40, A $\beta$ 42), and putative biomarkers of neurodegeneration (total Tau, phosphorylated Tau) and lipid peroxidation (isoprostanes) in AD
- f) To explore the pharmacodynamic effects of BMS-708163 on Cognition as assessed by an Executive Function Test Battery and the ADAS-cog
- g) To explore the pharmacodynamic effects of BMS-708163 on Function in daily living as assessed with the Alzheimer's disease Collaborative Study Activities of Daily Living scale (ADCS-MCI-ADL)
- h) To explore the pharmacodynamic effects of BMS-708163 on progression on the Global Clinical Dementia Rating (CDR global) (ie, progression to a global score of 1)
- i) To explore effects of BMS-708163 on brain amyloid content as measured via PET-amyloid imaging (AV-45) in a subset of subjects at specified sites
- j) To explore the pharmacodynamic effects of BMS-708163 on the subject-reported Outcomes in Cognitive Impairment (PROCOG), an instrument designed to assess severity of impairment and impact on subjects
- k) To assess Notch-mediated (safety related) effects of BMS-708163 on:
  - TFF3 plasma concentrations and its association with gastrointestinal safety signals
  - Lymphocyte mRNA levels of HES-1 and its association with clinical safety signals
  - The immune system (lymphocyte subpopulations; immunoglobulin serum levels)
- 2) To characterize pharmacokinetics (PK) and its relationship with pharmacodynamic (PD) effects:
  - Characterize plasma exposure of BMS-708163 and variability in a population with Alzheimer's disease
  - Characterize the relationship between BMS-708163 exposure and CSF biomarker response
  - Explore the relationships between BMS-708163 exposure and cognitive scores (ADAS- cog and others)

- Identify the source of exposure variability, including the correlation between polymorphisms of CYP enzymes (eg, CYP2C9 and CYP2C19) and exposures

#### 3 ETHICAL CONSIDERATIONS

#### 3.1 Good Clinical Practice

This study will be conducted in accordance with Good Clinical Practice (GCP), as defined by the International Conference on Harmonisation (ICH) and in accordance with the ethical principles underlying European Union Directive 2001/20/EC and the United States Code of Federal Regulations, Title 21, Part 50 (21CFR50).

The study will be conducted in compliance with the protocol. The protocol and any amendments and the subject informed consent will receive Institutional Review Board/Independent Ethics Committee (IRB/IEC) approval/favorable opinion prior to initiation of the study.

All potential serious breaches must be reported to BMS immediately. A serious breach is a breach of the conditions and principles of GCP in connection with the study or the protocol, which is likely to affect, to a significant degree, the safety or physical or mental integrity of the subjects of the study or the scientific value of the study.

Study personnel involved in conducting this study will be qualified by education, training, and experience to perform their respective task(s).

This study will not use the services of study personnel where sanctions have been invoked or where there has been scientific misconduct or fraud (eg, loss of medical licensure, debarment).

Systems with procedures that assure the quality of every aspect of the study will be implemented.

#### 3.2 Institutional Review Board/Independent Ethics Committee

Before study initiation, the investigator must have written and dated approval/favorable opinion from the IRB/IEC for the protocol, consent form, subject recruitment materials/process (eg, advertisements), and any other written information to be provided to subjects. The investigator or sponsor should also provide the IRB/IEC with a copy of the Investigator Brochure or product labeling, information to be provided to subjects and any updates.

The investigator or sponsor should provide the IRB/IEC with reports, updates and other information (eg, expedited safety reports, amendments, and administrative letters) according to regulatory requirements or institution procedures.

#### 3.3 Informed Consent

Investigators must ensure that subjects, or, in those situations where consent cannot be given by subjects, their legally acceptable representatives, are clearly and fully informed about the purpose, potential risks, and other critical issues regarding clinical studies in which they volunteer to participate. Freely given written informed consent must be obtained from every subject or, in those situations where consent cannot be given by subjects, their legally acceptable

representative, prior to clinical study participation, including informed consent for any screening procedures conducted to establish subject eligibility for the study.

Patients are required to have reliable study partners. A reliable study partner is defined as person who has a minimum of approximately 5 hours/week of direct contact with the study participant and who, in the judgment of the investigator is able to fulfill their study obligations (including being able to reliably describe and assess changes in the subject's condition).

[figure not shown]
The rights, safety, and well-being of the study subjects are the most important considerations and should prevail over interests of science and society.

Appendix 1 contains BMS procedures on obtaining informed consent from subjects, or, in those situations where consent cannot be given by subjects, their legally acceptable representative prior to participating in a clinical study. Procedures are described for all subjects, including those who are unable to give informed consent. The relevant procedures must be used whenever they are applicable (see subject selection criteria in Sections 4.2.1 and 4.2.2).

#### 4 INVESTIGATIONAL PLAN

# 4.1 Study Design and Duration

Figure 4.1-1: Study Schematic

### Study Schematic

Due to the early termination of this study, the duration of study treatment and performance of the protocol specified termination procedures will not be completed according to the design of the

protocol as previously described. All subjects still receiving study medication at the time of study termination by sponsor will be contacted by the site promptly, instructed to stop dosing, and will be asked to return for an End of Treatment a (EOT) Visit. When the data for that EOT visit has been entered into the EDC system, the treatment code will be provided to the study site. Subjects treated with avagacestat will be scheduled for the Post Treatment/Study Termination Safety Follow-up Visits (to occur 4 Weeks, 12 Weeks, and 24 Weeks after last dose). Subjects who were randomized to the placebo arm, and those enrolled in the observational cohort will be advised of their treatment group and told that no further assessments are required.

Avagacestat-treated subjects should be scheduled for a 4 Week, 12 Week, and 24 Week Post Treatment Safety Follow-up Visit as outlined in Table 6.1-4. All attempts should be made to complete the three Post Treatment/Study Termination Safety Follow-up Visits.

Avagacestat treated subjects participating in the long-term safety follow-up phase **for 12 weeks or less** should be scheduled for a 12 Week Post Treatment/Study Termination Safety Follow-up Visit, as well as for a 24 Week Post Treatment/Study Termination Safety Follow-up Visit for a comprehensive skin examination by a dermatologist (or dermatologic physician's assistant in the United States);

Avagacestat-treated subjects participating in the long-term safety follow-up phase **for greater than 12 weeks** should only be scheduled to return for the 24 Week Post Treatment/Study Termination Safety Follow-up Visit for a comprehensive skin examination by a dermatologist (or dermatologic physician's assistant in the United States).

Additionally all subjects who previously discontinued from this study (ie, those who did not participate in the long-term follow-up) but were exposed to greater than one month (31 days) of treatment with avagacestat should be contacted by the site and scheduled to complete the 24 Week Post Treatment/Study Termination Follow-up Visit for a comprehensive skin examination by a dermatologist (or dermatologic physician's assistant in the United States), irrespective of whether they received. a comprehensive skin examination with a dermatologist (or dermatologic physician's assistant in the United States) at the end of study treatment.

The study is a multi-center, randomized, double-blind, 2-arm, placebo-controlled, parallel-group study in patients with prodromal Alzheimer's disease to evaluate safety, tolerability, pharmacodynamic and pharmacokinetic effects of once-daily dosing of BMS-708163 for a minimum of 104 weeks (refer to Study Schematic in Figure 4.1-1 above).

The treatment period for the study will be a minimum of 104 weeks (2 years). Randomized subjects may continue in the study beyond 104 weeks of treatment (up to an estimated maximum of 220 weeks of treatment) until the last randomized subject has had the opportunity to receive study medication for approximately 104 weeks. Thus, given the recruitment period of approximately 27 months, the overall duration of study treatment is expected to last between 104 and 220 weeks for a given subject. The study treatment phase will end once the last randomized subject has completed approximately 104 weeks of treatment (estimated to occur by September, 2013). All subjects still receiving study medication at the time last patient last

Revised Protocol No.: 10

treatment is determined will end treatment and be followed in the Safety Follow-up Visits (4 Weeks and 12 Weeks post end of treatment visit; refer to Section 6.1.1.7).

After assessments of eligibility during the maximum 75 day screening period, subjects will undergo baseline safety and PD assessments. In a subset of subjects, at selected centers, subjects may be consented for 24-hour intensive PK assessments. In another subset of sites, subjects may be consented for PET imaging assessments at pre-specified visits (delineated in a separate, site-specific amendment).

All subjects will be randomly assigned in a double-blind manner to one of the following treatment groups: placebo or 50 mg BMS-708163 once daily. Treatment allocation will be balanced by symptomatic co-medication (ChEI): yes/no; Apolipoprotein E (APOE) Status (yes+/no-), consent for PET Imaging (yes/no) and consent for intensive PK assessments (yes/no).

All subjects will be treated with 50 mg during the study. Downward titration to 25 mg/day of BMS-708163 based upon the investigator's clinical judgment will only be allowed to manage limiting adverse events that emerge during the study. It is recommended that if down-titration does occur, the investigator consider a re-challenge to the highest tolerated dose for the subject to maximize A $\beta$  reductions. If the investigator does not attempt to re-challenge to the highest-tolerated dose, the investigator should contact the BMS medical monitor with the clinical rationale for not re-challenging at the higher dose. For the purposes of down-titration for tolerability issues, a dose range of 25 mg - 50 mg per day will be allowed during the treatment phase. A low dose of 25 mg per day is estimated to provide approximately > 10% A $\beta$  reduction, a level of reduction that may still provide a potentially meaningful reduction in brain A $\beta$  levels

All subjects will have trough PK assessments starting at the Week 2 visit and at all subsequent visits during the treatment period. An additional post-dose PK assessment will be completed at selected visits. At the time of CSF sample collection, both a blood and CSF sample will be collected for plasma and CSF PK analysis. These sample collections are outlined, in the Time & Events Schedule. A subset of subjects, at selected sites, will also complete one intensive 24-hour PK assessment on a day after they have been on treatment for 6 weeks and at a stable dose for at least two weeks (see Section 6.5.5.1). Safety and PD assessments will be performed as outlined in the Time & Events Schedule (see Section 6.1).

Subjects who do not meet the CSF inclusion criteria (CSF A $\beta$ 42 < 200 pg/mL or Total Tau/A $\beta$ 42 ratio of  $\geq$  0.39) but otherwise fulfill the study inclusion criteria may continue to be followed for rating scale visits but will not be randomized to any treatment arm. Given the projected CSF A $\beta$ 42 Screen Failure rate of 50%, it is estimated that approximately 100 subjects will enter the non-randomized observational group. Subjects in this non-randomized observational cohort will serve to provide prospectively collected comparison data regarding CSF cutoff values and progression to dementia rates. Once subjects in this observation cohort progress to a diagnosis of dementia they will be discontinued from the study.

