#### 4.2.1 Inclusion Criteria

#### 1) Signed Written Informed Consent

- a) Subjects (or legally acceptable representative as required by the IRB/IEC) and their study partners have provided a written signed informed consent form/forms (IRB/EC specific) prior to the initiation of any protocol required procedures;
- b) For sites participating in intensive PK testing an additional signed written consent by the subjects and their study partners has been obtained prior to the initiation of any intensive PK testing.

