# 8.4.3 Efficacy Analyses

Confidence intervals will be reported at the 95% level, if not otherwise specified.

In order to assess the predictive value of baseline CSF biomarkers (A $\beta$ 40, and A $\beta$ 42, total Tau, total Tau/A $\beta$ 42 ratio, and phosphorylated Tau) on progression to dementia, the relationship between each of CSF biomarker and time to progression to dementia will be assessed by separate stratified Cox proportional hazards model on the Randomized Sample. The Cox model will include treatment, age, gender, education and individual baseline biomarker as covariates and ApoE4 status and baseline status of acetylcholinesterase inhibitor treatment as stratified variables. The parameter estimate and 95% CI for the hazard ratio for one unit increase in the biomarker will be reported. Patients who do not have progression to AD will be censored on their last visit date.

In order to validate  $A\beta42$  screening cutoff point of 200 pg/mL, stratified logistic analysis will be carried out on the combined dataset of placebo group and observational cohort. The logistic model will have progression to AD (yes/no) as a binary dependent variable and age, gender, education and  $A\beta42$  screening value as covariates and ApoE4 status and baseline status of acetylcholinesterase inhibitor treatment as stratified variables.

Time to progression to dementia will be obtained from Kaplan-Meier maximum likelihood estimates for each treatment group on the Randomized Sample.

For each of the continuous efficacy outcome measurements (CDR-SB and ADAS-Cog, etc), the change from baseline to post-baseline scores (up to 24 months) over time from the Randomized Sample will be analyzed using a linear mixed effects model repeated measures (MMRM) with maximum likelihood estimation. The model will include treatment, time, baseline primary efficacy score, the interaction between baseline primary efficacy score and time, baseline MRI volume, APOE status, baseline status of acetylcholinesterase inhibitor treatment and the interaction between treatment and time as covariates. Time is classified into months (3, 6, 9, 12, 15, 18, 21, and 24) and treated as a categorical variable. An unstructured covariance matrix will be used to represent the correlation of the repeated measures within each subject. Model based adjusted mean change score from baseline (LS means) at each study month and 95% CI for the treatment difference will be reported.

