# 8.4.8 Other Analyses

#### 8.4.8.1 Biomarker Analyses

The mean change from baseline to each scheduled visit in the proposed biomarker measures (CSF biomarkers, plasma biomarkers and Volumetric MRI) will be analyzed based on Safety Sample. The analysis will make use of ANCOVA model, controlling for key covariates (APOE4 genotype, and concurrent AD medication use) and adjusting for corresponding baseline.

Specifically, for plasma TFF3 or CSF and plasma A $\beta$ 40 and A $\beta$ 42, the ANCOVA model will be applied to the log-transformed percentage of baseline measures. If multiple post-treatment time points were measured, a linear mixed effect model with fixed dose effect and time effect (repeated measures) will be used for the analysis.

For whole blood mRNA genes (HES-1), the gene expression level will be normalized to an internal housekeeping gene (eg, GAPDH) before applying statistical analysis. The change from baseline of the normalized gene expression levels will be fitted into the ANCOVA model.

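### Two of the four factors used to balance allocation, PET consent and intensive-PK consent, are in none of the planned analyses; in the linear models this can cost a little precision

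*Protocol*

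**What the plan says.** **Allocation.** Section 4.1 states: "Treatment allocation will be balanced by symptomatic co-medication (ChEI): yes/no; Apolipoprotein E (APOE) Status (yes+/no-), consent for PET Imaging (yes/no". The sentence goes on to a fourth factor, consent for intensive PK, so that its last two factors read: "consent for PET Imaging (yes/no) and consent for intensive PK assessments (yes/no". Crossed, four yes/no factors give 16 cells.

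**What the two consents are.** Both mark sub-study participation at chosen sites. On PK: "In a subset of subjects, at selected centers, subjects may be consented for 24-hour intensive PK assessments". On PET: "In another subset of sites, subjects may be consented for PET imaging assessments at pre-specified visits".

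**What the analyses contain.**
- MMRM for continuous efficacy outcomes (8.4.3): besides treatment, time and baseline terms, the list has "baseline MRI volume, APOE status, baseline status of acetylcholinesterase inhibitor treatment and the interaction between treatment and time as covariates". PROCOG follows the same approach (8.4.7).
- Cox model (8.4.3), for the predictive value of baseline CSF biomarkers, and logistic model (8.4.3), for the Aβ42 cutoff: both have "ApoE4 status and baseline status of acetylcholinesterase inhibitor treatment as stratified variables".
- Kaplan-Meier (8.4.3): by treatment group, with none of the four factors.
- APOE ANCOVA (8.4.6): names APOE4 only.
- Biomarker ANCOVA (8.4.8.1): "controlling for key covariates (APOE4 genotype, and concurrent AD medication use", plus the baseline value.
- Biomarker repeated-measures model (8.4.8.1): names dose and time only.

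PET consent and intensive-PK consent appear in none of these.

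**The concern.** When allocation is balanced on a factor that predicts outcome, the treatment estimate varies less from trial to trial than it would under simple randomization. A linear model credits that gain only if it contains the factor. Otherwise the factor's variance stays in the residual, and the reported standard error exceeds the true sampling variability.

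The protocol sets out the MMRM term by term, keeps two balancing factors, leaves out the other two and gives no reason. Both consents are offered only at some sites, and no planned model has a site term. They could therefore carry some between-site difference, but that is conjecture.

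At stake is the width of the drug-effect intervals for outcomes such as CDR-SB, ADAS-cog, volumetric MRI and the CSF markers. The possible error is loss of precision in a conservative direction, not bias.

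**Working it through.** **1. The plan's own figures.** The only sample-size figures are in 8.1. With 135 per group and a true AE rate of 3%, 1 − (1 − 0.03)^135 = 98.4%, as stated. The exact 95% CI for 13/135 is 0.052 to 0.159, against the stated (0.05, 0.16). Neither depends on covariates, so the present point leaves them unchanged. The protocol gives no effect size, SD or power for an efficacy outcome.

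**2. Inputs.** From the protocol: 135 per group, so N = 270; the four balancing factors; 95% confidence intervals; 25% progression per year (4.4). Not in the protocol, and so assumed: the share R² of residual variance that the two consents explain, how many subjects consent, and the mechanics of allocation (section 4.1 says only that it is balanced).

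**3. Linear models, by formula.** With balanced allocation, leaving the consents out multiplies the model standard error by k = 1/√(1 − R²). The true two-sided type I error at nominal 5% is 2[1 − Φ(1.96k)]. If the adjusted analysis had 80% power, the unadjusted one has Φ(1.960 + 0.842 − 1.960k).

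| R² | k | SE inflation | Type I error | Power |
|---|---|---|---|---|
| 0 | 1.0000 | 0% | 5.0% | 80.0% |
| 1% | 1.0050 | 0.5% | 4.9% | 79.7% |
| 2% | 1.0102 | 1.0% | 4.8% | 79.4% |
| 5% | 1.0260 | 2.6% | 4.4% | 78.5% |
| 10% | 1.0541 | 5.4% | 3.9% | 76.9% |

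The 80% is a reference value only; the protocol claims no efficacy power.

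**4. Linear models, by simulation.** There were 4,000 trials per setting, with N = 270, permuted blocks of four in 16 cells, each consent at 20% prevalence and a single-visit ANCOVA. A shift of b SD per consent gives R² = 0.32b²/(1 + 0.32b²), because 2 × 0.2 × 0.8 = 0.32.

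| b | R² | Mean SE, consents out | Mean SE, consents in | Ratio | Type I error, consents out |
|---|---|---|---|---|---|
| 0 | 0 | 0.1216 | 0.1216 | 1.000 | 5.2% |
| 0.2 | 1.3% | 0.1224 | 0.1217 | 1.006 | 5.0% |
| 0.4 | 4.9% | 0.1247 | 0.1217 | 1.025 | 4.4% |
| 0.6 | 10.3% | 0.1285 | 0.1217 | 1.056 | 3.9% |

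The ratios agree with the formula. At b = 0.6 the empirical SD of the estimate with the consents out was 0.1229, below the model SE of 0.1285, so the reported error is indeed too large. The MMRM itself was not simulated; the figures carry over to its treatment contrast at a given visit as an approximation.

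**5. Cox model.** There were 300 trials per setting, with 25% progression per year, two years' follow-up, an assumed hazard ratio of 0.7 and each consent at 20%.

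| Log HR per consent | SE, out vs in | Mean treatment log HR, out vs in |
|---|---|---|
| 0 | 0.1998 vs 0.1999 | −0.366 vs −0.367 |
| 0.5 | 0.1840 vs 0.1844 | −0.360 vs −0.372 |
| 1.0 | 0.1709 vs 0.1718 | −0.313 vs −0.360 |

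The standard error does not widen. Omission pulls the treatment log hazard ratio towards zero instead. The argument about width therefore does not transfer to this model.

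**The case against.** The strongest case against is that the two consents are logistical factors. A plausible reason to balance on them is to have both arms represented in each small sub-study, and nothing in the protocol says they predict cognition, atrophy or CSF markers. Section 8.4.8.1 calls APOE4 and AD medication the key covariates, which reads as a deliberate choice. The MMRM already conditions on baseline score, its interaction with time and baseline MRI volume, so a consent effect would have to act on change beyond those, and the upper end of the range looks unlikely. If site is the worry, a consent flag is a weak proxy. The SAP, not shown here, may add the terms or explain their absence.

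Most of this stands, and it is why the point is minor. It does not remove the mismatch: the protocol lists the MMRM terms, and two factors that shaped allocation are missing without a reason.

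A reader might infer more than the documents support:
- **That every planned model adjusts for exactly two of the four factors.** It does not: the APOE ANCOVA names one, Kaplan-Meier and the biomarker repeated-measures model name none, and the biomarker ANCOVA uses AD medication, which is not literally the ChEI factor.
- **That the drug effect on progression is affected in the same way.** The Cox model reports the hazard ratio for a unit of biomarker, with treatment as one covariate, and allocation does not balance biomarker level. The logistic model pools placebo with the observational cohort and has no treatment effect.
- **That PK consent may be signed after randomization.** Section 4.2.1 requires "an additional signed written consent by the subjects and their study partners has been obtained prior to the initiation of any intensive PK testing". It does not say that this may follow randomization, and section 4.1 implies that the status is known at allocation.

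**Conclusion.** The point holds as a minor matter of precision in the linear models: the MMRM in 8.4.3 and the biomarker ANCOVA and repeated-measures model in 8.4.8.1. Allocation is balanced on four factors, and two of them enter no analysis. If the consents are prognostic, the drug-effect intervals are about 0.5% to 2.6% too wide at R² of 1% to 5%, and 5.4% at 10%. If they are not, nothing is lost. These figures rest on an assumed R² and on allocation that achieves good balance; the protocol supplies neither.

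The direction is conservative, so it would be wrong to infer inflated type I error or an invalid comparison. Section 8.5 says that no efficacy endpoint is primary and that the sample size is not based on efficacy. Safety is tabulated by treatment (8.4.2), so the primary safety conclusion is untouched.

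**What to change.** In 8.4.3 (MMRM) and 8.4.8.1 (ANCOVA and repeated-measures biomarker model), add PET consent (yes/no) and intensive-PK consent (yes/no) as baseline covariates, using the values recorded at randomization. Leave PET consent out of analyses restricted to PET subjects, where it is constant. If the sponsor prefers to omit the factors, one sentence giving the reason would close the point.

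The Cox, logistic and Kaplan-Meier analyses need no change on this ground.

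The cost is a change of wording and about two model degrees of freedom out of roughly 265 (270 subjects less the few parameters of a simple ANCOVA). No new data are needed. Because these are design factors, adding them is not data-driven. Since section 8.5 allows unblinded interim results to reach some sponsor staff, a labelled sensitivity analysis with the two terms would suffice if a late change to the main model is unwelcome.
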